8.2 Randomization/Blinding

Phase 1:

The Phase 1 part of the study will be conducted as an open-label investigation.

Phase 2:

In the Phase 2 of the study, all subjects, investigators, clinical study site personnel and the blinded study monitor will be blinded to patient treatment assignment.

The dispensing Site Pharmacists are unblinded. An unblinded Study Monitor will be assigned to the study for confirming drug accountability and monitoring at the site's pharmacy. The Unblinded Pharmacist should take every precaution to prepare the study treatment in a blinded fashion and out of site from the Blinded site clinical staff. The Blinded Clinical Staff should be mindful of the steps in place to maintain the blind.

Treatment assignment for Phase 2 subjects should remain blinded to subjects, investigators, and clinical site staff until analyses of the primary and secondary safety and efficacy results of the study have been performed on the final, locked data through the end of post-SBRT follow-up for all subjects.

Only in the case of an emergency, when knowledge of the investigational product is essential for the clinical management or welfare of the subject, may the Investigator unblind an individual subject's treatment assignment prior to the completion of the primary and secondary safety and efficacy analyses. The Investigator will, whenever possible, discuss options with the Medical Monitor or appropriate Sponsor/CRO study personnel before unblinding. If the blind is broken for any reason and the Investigator is unable to contact the Sponsor prior to unblinding, the Investigator must notify the Sponsor/CRO as soon as possible following the unblinding incident without revealing the subject's study treatment assignment, unless the information is important to the safety of subjects remaining in the study.

Randomization codes are generated and assigned using a Randomization and Trial Supply Management (RTSM) system. Electronic access to the randomization codes will be granted for unblinded pharmacy team members and unblinded CRAs.

8.3 Populations for Analyses

The Phase 1 population will include all subjects who receive at least one dose of GC4711. The DLT evaluable population includes all patients in the Phase 1 population who have received all five GC4711 doses, are followed for 30 days post SBRT and were DLT free or experienced a DLT. The Phase 2 intent-to-treat population includes all subjects randomized and is used in disposition. Safety and efficacy analyses for Phase 2 will be performed on a modified intent-to-treat population that includes all randomized subjects who receive at least one dose of GC4711 or placebo.

8.4 Subject Disposition

The number of subjects included in each study population will be summarized by treatment group. Subjects excluded from the intent-to-treat population will be listed by randomized treatment group.

The number and percentage of subjects who complete or who prematurely discontinue during the treatment periods will be presented. Screen failures (i.e., screened but not randomized subjects) and the associated failure reasons will be tabulated overall. Reasons for premature discontinuation from the treatment period as recorded on the termination page of the eCRF will be summarized (number and percentage) by treatment group for all randomized/registered subjects.

8.5 Statistical Analyses

The statistical analysis plan will be finalized prior to database lock and will include a more detailed description of the statistical analyses described in this section. Should the statistical analysis plan and the protocol differ with respect to analytic conventions, the statistical analysis plan supersedes the protocol. Given the study has not been powered for formal hypotheses testing, all P-values should be considered descriptive in nature. As such no alpha adjustment for multiple testing is planned.

All time to event endpoints will be measured from date registration (Phase 1) or randomization (Phase 2).

Primary Endpoints:

Phase 1: DLT defined in Section 7.5.

Phase 2: The difference in in-field tumor response between GC4711 and placebo through Month 6 following SBRT will be estimated, and a two-sided 90% confidence interval constructed around the difference using the large sample confidence interval with limits $\pm Z.05 \sqrt{[(p1*(1-p1)/n + p2*(1-p2)/m)]}$ of the point estimate where p1 and p2 are the response rates and n and m the corresponding number of patients in each arm. In addition, a Fisher's Exact test will be performed but should be considered descriptive in nature. Phase 2: Percent reduction of in-field tumor response at Month 6 compared to baseline.

Secondary Efficacy Endpoints:

Phase 1: All Phase 1 efficacy endpoints will be summarized descriptively.

Phase 2: Response rate (PR+CR at any time during the study) per RECIST 1.1 will be compared using the same methodology as the primary endpoint.

In-field tumor response at Months 6, 12, 18 and 24 will be compared for the two treatment arms using a t-test at each timepoint and corresponding two-sided 90% confidence intervals constructed about the difference. The maximum reduction for each patient observed at any time will be analyzed similarly.

Progression-free survival (PFS) will be compared using a hazard ratio along with the associated 2-sided 90% confidence interval, using an un-stratified Cox's proportional hazard model and further characterized by Kaplan-Meier curves as well as the median and survival probability at

representative times (e.g. at 2, 4, 6, 4 etc. months). A log-rank test comparing treatment arms based on the score statistic from the Cox regression will also be provided. Patients who have not progressed or died will be censored at their last evaluable response assessment.

Overall Survival (OS) as well as duration of local and regional control will be analyzed using the same approach as PFS. For OS, patients who have not died as of the time of analysis will be censored the date last known to be alive. For duration of local and regional control, local enlargement, marginal failures, involved lobe failure, or local relapse will be considered failure events for local control. Regional failure with nodal progression (new lesions) in the mediastinum will be a failure event for regional control. Distant metastases from the index lung cancer or a second primary tumor are not considered local progression. Patients who die with lung cancer, but who do not have documented local progression will be considered non-failures for local progression and will be censored on the day of their death. Patients who die without progressive lung disease and have no documented local progression will be considered non-failures for local progression and will be censored on the day of death.

Distant-metastases rate will be summarized descriptively.

Exploratory Endpoints

All safety endpoints will be summarized descriptively including mean and mean change from baseline for continuous endpoints and n and percent for categorical endpoints.

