Inclusion and exclusion criteria ^e	X									
Registration/Randomization (Phase 1/Phase 2) ^e	X									
Medical history (includes smoking history)	X									
Demography	X									
Complete PE including height and weight	X								X	
ECOG Performance Status	X								X	
Vital signs ^f	X	X	X	X	X	X				
PK Blood samples ^g		X	X							
12-lead ECG ^h	X	X		X						
AE/SAE review ⁱ		X	X	X	X	X	X	X	X	
Concomitant medications/treatments and smoking review ^j	X	X	X	X	X	X		X	X	X
Survival Status								X	X	X
Serum pregnancy test (WOCBP only)	X									
Serum chemistry panel	X						X			
Complete blood count	X						X		X	
PT/INR, aPTT	X									
PFTs – SpO ₂ , FEV1, FVC and DLCO ^{k, n}	X								X	
CT chest for pneumonitis scoring ^k	X								X	X
CT (chest, abdomen, pelvis) ^k	X								X	X
GC4711/Placebo IV infusion ^l		X	X	X	X ^l	X ^l				
SBRT administration ^m		X	X	X	X ^m	X ^m				

AE = adverse event, BP = blood pressure, CBC = complete blood count, CT = computed tomography, CTCAE = Common Terminology Criteria for Adverse Events, DLCO = diffusion capacity of lung for carbon monoxide, ECG = electrocardiogram, ECOG PS = eastern cooperative oncology group performance status, FEV1 = forced expiratory volume in 1 second, FU = Follow-up, , IV = intravenous, PE = physical examination, PET = positron emission tomography, PFTs = pulmonary function tests, PK = pharmacokinetics, SAE = serious adverse event.

- a Screening evaluations should occur within 21 days of Treatment Day 1, except where otherwise noted
- b The Day 12 visit should occur 7 days after the last dose of SBRT \pm 5 days
- c The 30- and 90- day post SBRT completion visits should occur on or within 7 days after target date and may be performed remotely via telemedicine visits. The Months 6 and 12 post SBRT completion visits should occur \pm 7 days of target date.
- d The Month 18 and 24 post SBRT visits should occur \pm 14 days of target date.
- e Registration/Randomization should occur after all screening assessments are performed, eligibility is confirmed, and within 7 days of the first dose of SBRT. Confirmation of eligibility should include confirmation of diagnosis, histology and exclusion of distant disease by standard practice.
- f BP and HR should be taken prior to each infusion, monitoring possible hypotensive symptoms, please repeat before going from infusion to radiation site.

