Secondary	
- To determine the degree of in-field tumor response at 6, 12, 18 and 24 months following completion of SBRT- To compare progression-free survival, overall survival, local tumor control, and distant metastasis rates over a 2-year follow up period for SBRT plus GC4711 or placebo- To assess durability of in-field complete or partial responses- To determine acute lung toxicity after SBRT + GC4711 compared to SBRT + placebo for early-stage NSCLC- To evaluate the rate of acute and late radiation toxicities for SBRT + GC4711 compared to SBRT + placebo- To assess the relationship between clinical, functional and radiographical lung function changes observed after SBRT 
- Percent reduction of in-field tumor at Months 6, 12, 18 and 24- Number of participants with CR+PR- Number of participants experiencing grade 1 or higher in diffusion capacity of lung for carbon monoxide (DLCO), measured by RTOG scale, at 6-months after the completion of SBRT- Measurement of the following parameters over 12 months after SBRT
- Changes in pulmonary function testing (pulse oximetry [SpO₂], forced vital capacity [FVC], first expiratory volume in the first second [FEV₁], DLCO), clinical and radiological pneumonitis scoring- Reporting of observed adverse events in patients- Late Radiation Toxicities (including clinical and radiographic pneumonitis, esophagitis, pulmonary fibrosis, rib fractures, plexopathy, cardiac and vascular events) up to 12 months following the completion of SBRT- Measurement of the following parameters over 24 months after SBRT
- Progression Free Survival (PFS)- Overall Survival (OS)- Local and regional control- Distant Metastases (DM) rate

OBJECTIVES	ENDPOINTS
	-

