Phase 2: After the SRC has confirmed acceptable safety in the Phase 1, a Phase 2, randomized, placebo-controlled study phase will be initiated, wherein approximately 66 subjects referred for SBRT with early stage large and/or central localized NSCLC will be randomized in a 1:1 ratio to receive either GC4711 100 mg or placebo given IV over 15 minutes on each day that SBRT is given, beginning the day of the first fraction of SBRT and ending the last day of SBRT,. SBRT is administered within 180 minutes (3 hours) of the end of the GC4711 infusion. A minimum of 18 hours and a maximum of 96 hours are permitted between fractions. All fractions should be given within 10 calendar days (+3 days in the case of a holiday or technical issue).

All subjects will be evaluated for changes in the in-field tumor for 24 months following completion of SBRT. The primary endpoint will evaluate the percentage of patients with complete or partial in-field tumor response through 6 months following SBRT. In addition, as a secondary endpoint, the percent of subjects with overall responses (PR + CR) per RECIST 1.1 will be evaluated.

All subjects will be evaluated by changes in the diffusion capacity of lung for carbon monoxide (DLCO), as assessed by the RTOG grading scale monitored at 6 months and 12 months. The secondary endpoints will evaluate all lung function parameters. Pneumonitis will also be assessed both clinically and radiographically (CTCAE 5.0).

All subjects will be followed for 30 days post SBRT completion for treatment related adverse events, 90 days post SBRT completion for acute radiation toxicity and for 12 months post SBRT completion for late radiation toxicity, and will be followed for 24 months post SBRT completion for local and regional disease control (LC), Progression Free Survival (PFS), Overall Survival (OS) and Distant Metastases (DM) rate.

Detailed information on the Radiation Therapy Quality Assurance (RTQA) (Phase 1 only) and dose-volume exposure, concomitant medications and existing obstructive lung disease will be collected for pneumonitis-risk analyses.

Pharmacokinetic (PK) sampling and cardiac monitoring will be performed on each subject with two separate doses of GC4711 (or placebo) collecting blood samples pre-infusion post-infusion and 24 hours post-infusion (Phase 1 only) for each.

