4.2 Study Duration for Participants

The study duration for participants is expected to be approximately 25 months. This includes a 21-day screening period, a treatment period of approximately 5-10 days, and long-term follow-up for 24 months. All subjects are evaluated 30 days after SBRT and 6, 12, 18 and 24 months post-SBRT.

If a participant experiences progressive disease prior to 24 months post-SBRT completion, they will continue for survival follow-up until end of study (24 months following the last administration of SBRT). No additional tumor assessments will be required after progression; however, adverse events for long term radiation toxicities will continue through 12 months post SBRT completion and survival follow up will continue through 24 months post SBRT completion.

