7.1 Efficacy Assessments

Tumor Assessment (RECIST)

Staging imaging will be performed by CT scan according to the SoA. Tumor Response will be evaluated at each time point. Radiographic response will be measured according to RECIST 1.1 (Eisenhauer 2009). All imaging will be interpreted locally by the investigational site radiologist. The same method of imaging used at baseline must be used at each follow up evaluation for treatment response.

The number of subjects exhibiting PR, CR and PR+CR will be reported at Months 6, 12, 18 and 24.

RECIST 1.1 Tumor Response Evaluation Definitions of the criteria used to determine objective tumor response for target lesions (Eisenhauer, 2009)	
Complete Response (CR):	Disappearance of all target lesions. Any pathological lymph nodes (whether target or non-target) must have reduction in short axis to <10 mm.
Partial Response (PR):	At least a 30% decrease in the sum of diameters of target lesions, taking as reference the baseline sum diameters.
Progressive Disease (PD):	At least a 20% increase in the sum of diameters of target lesions, taking as reference the smallest sum on study (this includes the baseline sum if that is the smallest on study). In addition to the relative increase of 20%, the sum must also demonstrate an absolute increase of at least 5 mm. (Note: the appearance of one or more new lesions is also considered progression)
Stable Disease (SD):	Neither sufficient shrinkage to qualify for PR nor sufficient increase to qualify for PD, taking as reference the smallest sum diameters while on study.

Definitions for Response Evaluation

Progression-Free Survival

Progression-free survival (PFS) is defined as the time from the date of registration (Phase 1) or randomization (Phase 2), to first occurrence of local and/or regional NSCLC progression, distant metastases from NSCLC, second primary tumor, or death due to any cause, whichever occurs first. Patients without progression and who did not die are censored at their last evaluable tumor response assessment.

Local and Regional Control

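### The Month 12-24 in-field t-tests have no rule for scans after progression, and the planned Kaplan-Meier for local control overstates the share of patients who fail locally

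*Combined protocol and SAP*

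**What the plan says.** **Endpoint and test.** Section 3 lists as a Phase 2 secondary endpoint: "Percent reduction of in-field tumor at Months 6, 12, 18 and 24". Section 8.5 states: "In-field tumor response at Months 6, 12, 18 and 24 will be compared for the two treatment arms using a t-test at each timepoint", with two-sided 90% confidence intervals. It also plans analyses of maximum reduction and of response at any time.

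**Scanning.** Section 4.1 states: "All subjects will be evaluated for changes in the in-field tumor for 24 months following completion of SBRT". Table 1 marks the chest, abdomen and pelvis CT at Months 6, 12, 18 and 24, and its footnotes make no exception for progression. Section 4.2 states: "No additional tumor assessments will be required after progression". It adds that "survival follow up will continue through 24 months post SBRT completion". Progression in the PFS definition of Section 7.1 (Efficacy Assessments) runs "to first occurrence of local and/or regional NSCLC progression, distant metastases from NSCLC, second primary tumor, or death due to any cause", so it includes events outside the irradiated field.

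**New anti-cancer therapy.** The Synopsis, Table 1 footnote j and Section 6.1 (Collection of Concomitant Medications) have it recorded to 24 months or to progression. Section 7.1 (Safety Assessments, Lung function) has it recorded through 24 months.

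**Local control.** Section 8.5 analyses it in the same way as PFS (Cox model and Kaplan-Meier), with patients who die without documented local progression censored at death.

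**Deferral.** Section 8.5 adds: "The statistical analysis plan will be finalized prior to database lock and will include a more detailed description of the statistical analyses". No separate SAP is part of the document reviewed.

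**The concern.** A patient with a distant metastasis or a second primary may stop being scanned while the irradiated lesion can still be measured. A patient whose irradiated lesion regrows may also stop. If scans stop, the later t-tests compare patients who are alive and progression-free, plus those first seen to progress at that visit. Living patients who progressed earlier drop out, and the per-visit test makes no use of their earlier scans. If scans continue at some sites, lesion sizes measured after new therapy enter the test, and the sections differ on whether that therapy is recorded.

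Section 8.1 says the sample size is also meant to yield efficacy data for planning future studies, so a distorted Month 12-24 estimate could carry forward. For local control, the Kaplan-Meier complement is easily read as the proportion of patients who fail locally. It is not that proportion when deaths are censored.

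**Working it through.** **1. The plan's own figure.** Section 8.1 gives a maximum 90% half-width of 21.2% for the primary response difference: 1.645 x sqrt(0.25/30 + 0.25/30) = 0.2123. It reproduces. The documents give no figure for the Month 12-24 t-tests.

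**2. Patients available.** Inputs are 30 evaluable per arm (Section 8.1) and 2-year OS 70% and PFS 55% (Section 2.1). Constant hazards are assumed, with no loss to follow-up after Day 90. Alive at month t: 30 x 0.70^(t/24). Scanned at t if scanning stops at progression: 30 x 0.55^((t-6)/24) x 0.70^(6/24), because the scan that first shows progression still counts.

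| Visit | Alive | Scanned if scanning stops |
|---|---|---|
| Month 12 | 25.1 | 23.6 |
| Month 18 | 23.0 | 20.4 |
| Month 24 | 21.0 | 17.5 |

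At Month 24, 9.0 of the 12.5 patients missing per arm have died; the scanning rule accounts for 3.5. With PFS of 50-60%, also cited in Section 2.1, the scanned number is 16.3-18.7.

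**3. Direction of the bias, by simple arithmetic (assumed inputs).** Suppose failed lesions differ from controlled ones by g points of shrinkage, and local failure is independent of death. With 2-year control c, the share controlled at Month 24 is c among the living. Among those scanned it is c^0.25, since only failures after Month 18 are still seen. For c = 0.90, that is 0.900 against 0.974.
- Mean shrinkage in one arm is overstated by (0.974 - 0.900) x g: 2.2 points for g = 30 and 3.7 for g = 50.
- Control 90% v 97.5%, g = 50: the difference among the living is 0.075 x 50 = 3.75; among the scanned it is (0.9937 - 0.9740) x 50 = 0.98. That is 2.8 points toward zero.
- Over 91-99.9% control with GC4711 and g = 30-90, the shift is 0.2-6.6 points toward zero.
- With 70% placebo control (the other figure in Section 2.1) it is 4.4-19.3 points. That setting implies PFS of at most 0.70 x 0.70 = 49%, just under the cited range.
- Control 90% in both arms, with 10 extra points of shrinkage only in controlled lesions: 0.900 x 10 = 9.0 among the living, 0.974 x 10 = 9.7 among the scanned. The shift is away from zero.

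**4. A fuller model (assumed).** Eight settings were simulated. Log size ratio at Month 6 was normal with mean -0.45 (placebo) or -0.65 (GC4711), SD 0.30 or 0.40, with mean slope -0.05 per visit. In-field progression was set at 1.2 x nadir (9.6-10.4% of placebo patients by Month 24). Other hazards were solved to 55% PFS and 70% OS, either independent of size or linked to it, with death hazard the same before and after progression or mostly after it. At Month 24 the difference was 0.1-2.8 points lower among the scanned than among the living (extremes 8.57 read as 8.44, and 10.83 read as 8.05). The 90% half-width was 9.0-10.9 points. Placebo mean shrinkage was overstated by 1.0-4.6 points. With equal arms there was no between-arm bias.

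**5. Local control.** With a = -ln(LC), b = -ln(OS) and independent constant hazards, cumulative incidence = a/(a+b) x (1 - LC x OS).
- LC 0.90, OS 0.70: 0.1054/0.4620 x 0.37 = 8.4%, against 10% from 1-KM.
- LC 0.80 (assumed): 0.2231/0.5798 x 0.44 = 16.9%, against 20%.

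**The case against.** Section 4.1 states a general schedule and Section 4.2 a specific rule for patients who progress, so the second can be read as an exception to the first. That stands. The text is not an outright contradiction and Section 4.2 does not forbid scans. But because it only removes the requirement, sites may differ, and Section 8.5 still names no analysis set. A later SAP can choose an analysis but cannot recover scans that were not taken.

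A reader might infer that the treatment difference is pulled toward zero by a known amount. The documents do not support this: they give no shrinkage distribution, SD or arm-specific failure rate. All eight modelled settings assume a uniform shift in size that also reduces in-field progression under GC4711. In the most extreme one, 5.8% of placebo patients already meet the progression threshold at Month 6. Other inputs give larger shifts or reverse the sign.

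A reader might also put the fall from 30 to 17.5 down to the scanning rule; most of it is death.

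It is also fair to say that maximum reduction and any-time response keep earlier scans, that PFS and local control capture in-field failures, and that the primary endpoint is barely touched because Month 6 is the first scheduled tumour scan after SBRT. On local control, censoring at death is stated openly, and the gap at 90% control is 1.6 points, about half a patient per arm of 30.

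**Conclusion.** The concern holds as a minor one. The sections on scanning after progression must be reconciled, as must those on recording new therapy, and the Month 12-24 tests need a stated set of scans. If scanning stops at progression, about 3.5 living patients per arm are missing at Month 24 (constant hazards, 55% PFS, 70% OS). Mean shrinkage then tends to look too good, and the between-arm difference can be biased. The modelled shift of 0.1-2.8 points lies inside a half-width of 9-11 points and rests wholly on assumed shrinkage models, so it illustrates the problem and does not estimate its size.

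For local control, 1-KM overstates the share failing: 10% against 8.4% under independent constant hazards. It would go too far to infer that the Cox analysis is invalid, since its hazard ratio stands as a cause-specific one. These are secondary endpoints, and Section 8.5 calls all P-values descriptive.

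**What to change.** 1. Reconcile Section 4.1 and Table 1 with Section 4.2 on imaging after progression, and the Synopsis, Table 1 footnote j and Section 6.1 with Section 7.1 on recording new therapy. State which scans enter the Month 12-24 analyses, including any taken after progression or new therapy. Which scanning rule to adopt is for the sponsor. This is a clarification and adds scans only if the sponsor resolves it that way.

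2. Keep the t-tests. Add one supporting repeated-measures analysis of percent change using all scans (arm, visit, arm-by-visit, baseline size; 90% interval per visit). Label it as assuming missing-at-random and as describing tumour size as if no one had died. It is not expected to be more precise. In the modelled settings its root mean squared error against the difference among the living ranged from 10% lower to 14% higher than the t-test's at Month 24. It overstated that difference by up to 2.6 points where death was linked to progression or tumour size. Interval coverage was not examined. It therefore belongs beside the t-tests and not in their place.

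3. Report the cumulative incidence of local failure (Aalen-Johansen), with death as a competing event, beside the cause-specific Cox hazard ratio.

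Items 2 and 3 need only SAP wording and programming, on data already planned for collection.
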